2.3 Study Design

This is an open-label, randomized, crossover study with a visit to initiate a 4-week diet lead-in period at Day -28 (visit 1), up to 3 screening visits on Days -14, -7 and -3 (visits 2, 3, and 3b [only for subjects needing an additional TG measurement to qualify for inclusion]), a randomization visit on Period 1 Day 1 (visit 4), two visits at the end of each treatment period (Days 22 and 29; visits 5 and 6 in treatment period 1 and visits 9 and 10 in treatment period 2), and 2 visits after a 28-day washout period to establish baseline for treatment period 2 on Days -7 and 1 (visits 7 and 8). At visit 4, subjects are randomly assigned to a treatment sequence, and they will receive the first dose of study product during each treatment period at the clinic along with a therapeutic lifestyle changes (TLC)-compliant meal replacement bar. Subjects will continue to take their study product daily for 28 days and return to the clinic on Days 22 and 29 in each treatment period for evaluation. Pharmacodynamic assessments including fasting concentrations of TG and lipoprotein cholesterol, apolipoproteins, hs-CRP, PCSK9, as well as plasma phospholipid omega-3 fatty acids will be completed at the beginning and end of each treatment period (depending on the parameter, beginning and end may refer to multiple visits). Fatty acids from red blood cells (RBC) will be analyzed from samples collected during treatment 1 only (visits 4, 5 and 6).

Each subject will receive a 4-g/day dose of each treatment, according to randomized crossover design. Study product is provided in 1 g capsules.

- 4 g/day MAT9001 (2 g with each of two meals)
- 4 g/day Vascepa (2 g with each of two meals)

The first doses during each treatment period will be administered at the clinic as two capsules taken along with a TLC-compliant meal replacement bar. The remaining capsules will be sent home with the subjects with instructions to take two capsules twice daily with meals each day of the treatment period.

A schedule of procedures is presented in Table 1.

Table 1: Schedule of Events

Clinic Visit ^a	Screening				Treatment 1			WO	Treatment 2		
	1	2	3	3b	4	5	6	7	8	9	10
Day	-28	-14	-7	-3	1	22	29	-7	1	22	29
Informed consent/HIPAA ^b	X										
Clinic visit procedures ^c	X	X	X		X	X	X	X	X	X	X
Medical history ^d	X										
Chemistry panel		X			X		X		X		X
Hematology		X			X		X		X		X
HbA1c ^e		X									
TSH ^f		X									
hs-CRP			X		X	X	X	X	X	X	X
hs-CRP confounder checklist			X		X	X	X	X	X	X	X
Archive samples ^g					X		X		X		X
Urinalysis		X					X				X
Urine pregnancy test ^h		X			X				X		
Physical examination			X								
12-lead ECG			X				X				X
TLC diet instruction/reinforce ⁱ	X	X	X	X	X	X	X	X	X	X	
MEDFICTS questionnaire ^j	X	X			X		X	X	X		X
Provide/review study instructions	X	X	X	X	X	X	X	X	X	X	X
Randomization					X						
Start washout period ^k							X				
Dose study product + TLC bar ^l					X				X		
Dispense study product					X	X			X	X	
Collect SP/assess compliance						X	X			X	X
Fasting Omega-3 fatty acids ^m					X	X	X		X	X	X
Fasting lipids ⁿ	X	X	X	X	X	X	X	X	X	X	X
Fasting apolipoproteins ^o					X		X		X		X
Fasting PCSK9					X		X		X		X
Treatment-emergent AEs ^p					X	X	X	X	X	X	X

Abbreviations: AE, adverse event; ECG, electrocardiogram; HbA1C, hemoglobin A1c; HIPAA, Health Insurance Portability and Accountability Act; hs-CRP, high-sensitivity C-reactive protein; MEDFICTS, Meats, Eggs, Dairy, Fried Foods, In baked goods, Convenience foods, Table fats, Snacks; PCSK9, proprotein convertase subtilisin kexin type 9; SP, study product; TLC, Therapeutic Lifestyle Changes; TSH, thyroid stimulating hormone; WO, washout.

- ^a To adjust for subject scheduling, the allowable window to complete all screening procedures will not exceed 42 days with a minimum of 48 hours between all visits. If the subject is already following a Therapeutic Lifestyle Changes (TLC) diet at visit 1 supported by the Meats, Eggs, Dairy, Fried Foods, In baked goods, Convenience foods, Table fats, Snacks (MEDFICTS) score, they can proceed directly to visit 2 procedures. A TLC diet lead-in of 14 days prior to the qualification visit (visit 2, Day -14) will be required. A window of ±2 days will be allowed for visits on Day 22 (visits 5 and 9); the window for visits on Day 29 (visit 6 and 10) will be minus 2 days only, i.e., Days 27, 28 or 29. The washout period between treatments (between visits 6 and 7) should be a total of at least 28 days, but not more than 35 days.
- ^b Health Insurance Portability and Accountability Act (HIPAA) authorization for disclosure of protected health information. Signed document authorizes the use and disclosure of the subject's Protected Health Information by the Investigator and by those persons who need that information for the purposes of the study. If a subject does not require a dietary lead-in based on MEDFICTS score, the first two visits should be combined.
- ^c Study procedures include assessments of height (visit 1 only), weight, vital signs (heart rate and blood pressure), waist circumference, evaluation of inclusion and exclusion criteria (visits 1 - 4), review of continuation requirements (visits 5 - 10) and concomitant medication use.
- ^d Medical history will be completed with visit 1 procedures.
- ^e Glycated hemoglobin (HbA1c) will be analyzed only for subjects with a history of type 2 diabetes mellitus OR a fasting glucose concentration ≥126 mg/dL.
- ^f Thyroid stimulating hormone (TSH) will be assessed at screening visit 2 (Day -14). Uncontrolled hyper- or hypothyroid conditions are exclusionary based on the opinion of the Investigator.
- ^g Plasma and/or serum and/or blood cells will be collected, processed and stored for possible later analysis of non-genetic

-
- analytes for assessment of cardiometabolic health and/or lipid metabolism.
- ^h A urine pregnancy test will be performed for all women <60 years of age.
 - ⁱ Subjects will receive instruction on the TLC diet at the first screening visit and instructions will be reinforced for the duration of the study. Subjects will continue to follow the TLC diet during the washout between treatment periods.
 - ^j The MEDFICTS Dietary Assessment Questionnaire will be completed at screening to determine whether the subject is already following a TLC diet, and it will be completed periodically during the study to evaluate compliance with the TLC diet instructions. If the subject is not following a TLC diet at screening, a TLC diet lead-in of 28 days prior to the first treatment phase (visit 4, Day 1) will be required.
 - ^k At the conclusion of visit 6, subjects will begin a washout period of at least 28 days, but not more than 35 days, prior to visit 7.
 - ^l The first dose of the study product for that treatment period will be administered at the clinic with a TLC-compliant meal replacement bar.
 - ^m Fasting plasma and plasma phospholipid levels of eicosapentaenoic acid (EPA), docosahexaenoic acid (DHA), docosapentaenoic acid (DPA) and total omega-3 fatty acids will be assessed. Fatty acids from red blood cells (RBCs) will be analyzed from samples collected at visit 4, 5 and 6 only (treatment 1).
 - ⁿ Fasting levels of triglyceride (TG), total-cholesterol (total-C) and high-density lipoprotein cholesterol (HDL-C) will be measured, non-HDL-C, low-density lipoprotein cholesterol (LDL-C), very low-density lipoprotein cholesterol (VLDL-C) will be calculated. A minimum of 50% of enrolled subjects will have a TG value ≥ 200 -499 mg/dL as assessed at screening.
 - ^o Fasting levels of apolipoprotein (Apo) A1, Apo B and Apo C3 will be measured.
 - ^p Treatment-emergent AE's will be assessed at visits 4 through 10. AEs that occur prior to visit 4 will be considered medical history. AEs will also be collected from spontaneous subject reporting at any time during the study.

3 RANDOMIZATION PROCEDURES

This is an open-label study. Eligible subjects will be randomly assigned using a computer-generated randomization scheme stratified by TG group (TG values <200 mg/dL or TG values \geq 200-499 mg/dL). If a subject meets all inclusion and none of the exclusion criteria, the following steps should occur at visit 4 (Day 1):

1. Site will utilize an Interactive Web Response System to randomize the subject. The randomization number/sequence will be recorded with the subject's source documentation.
2. Site will complete a Master Study Product Log upon dispensement of study product, which is a list of all study product received and dispensed at the site.

4 GENERAL STATISTICAL CONSIDERATIONS

All analyses described in this plan are considered *a priori* analyses in that they have been defined before locking the database. All unplanned statistical analyses, if any, designed after the SAP is finalized, will be considered *post hoc* analyses and will be applied as exploratory methodology. All *post hoc* analyses will be identified as such in the clinical study report in the changes to the planned analyses section, as appropriate. Instances where the details of the SAP differ from the protocol, the SAP will be used as the source of the procedures for data analyses.

All statistical tests will be tested at $\alpha = 0.05$, 2-sided significance level, unless otherwise stated. Descriptive statistics for continuous variables will include number of subjects/observations (N, n), mean, median, standard deviation (SD), minimum, maximum, and first [25th percentile] and third [75th percentile] quartiles (Q1, Q3), unless otherwise noted. Confidence intervals will be presented where appropriate. Descriptive statistics for categorical variables will consist of frequency and percentage.

Summary statistics will be presented as follows: N and n will be presented without any decimals, minimum and maximum to the same precision as the reported values, means and median to 1 more level of precision than the reported values, and SD to 2 more levels of precision than the reported values, or as otherwise decided upon by the study team. Data listings will be sorted by subject number.

All statistical analyses will be conducted using SAS[®] Version 9.4 (SAS Institute Inc., Cary, NC) or later using procedures appropriate for the particular analysis.

5 ANALYSIS POPULATIONS AND DATASETS

5.1 Definition of Analysis Populations

Statistical analysis and data tabulation will be performed using the following subject populations unless specified otherwise:

- Intention-to-treat (ITT) population;
- Safety population;
- Pharmacodynamic (PD) population;
- Per protocol (PP) population.

The ITT population will include all subjects who are randomized to a treatment sequence.

The safety population will include subjects who are randomized and receive at least one dose of any study treatment. This will be the primary population for safety analyses.

The PD population will include subjects for whom the estimation of PD parameters will be possible for 2 periods. This will be the primary population for PD analyses. PD parameters cannot be estimated accurately for subjects who have been off of study drug for an extended period prior to measurements. The half-life of EPA from Vascepa is approximately 89 hours (Vascepa Prescribing Information, accessed 01Dec20) and that for EPA from MAT9001 administered in the fed state is approximately 27 hours (MAT-001 clinical study report, 07Jul20). Measurements will not be used for PD estimation from samples obtained from subjects who have been off of study drug for 3 days (72 hours) or more.

The PP population will include all subjects who are included in the PD population for whom compliance for both study periods was at least 80%, and for whom no clinically important protocol violations or deviations occurred during the trial. All decisions regarding inclusion in the PP dataset will be made and documented prior to database lock.

5.2 Handling of Missing Data

Multiple imputation (MI) will be used in the ITT analyses to impute missing data for the lipoprotein cholesterol, apolipoproteins, PCSK9, hsCRP, and omega-3 fatty acid outcome variables. The MI procedure in SAS will use the Markov chain Monte Carlo (MCMC) method with a single chain to create at least 5 imputations or more in order to obtain a stable result. Each iteration is analyzed and the final result reported will be the summarized values using the MIANALYZE procedure in SAS.

No imputation will be done for missing data in the safety, PD, or PP analyses. Data that are excluded from the descriptive or inferential analyses will be included in the data listings. This will include those measurements from excluded subjects or measurements from unscheduled visits/collections. If values are reported as below or above the limit of quantitation, they will be set to the quantitation limit and included in the summaries and analyses. For calculations of average values, all values provided will be included, even if only 1 value of the average is reported.

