#### **9.4 Early Termination Procedures**

The term “Early Termination” refers to a subject’s non-completion of the study. Should a subject decide to withdraw, all efforts will be made to complete and report observations as thoroughly as possible. In the event that a subject is withdrawn from the study, the reason for the withdrawal and the party who initiated the withdrawal (subject or Investigator) will be documented. Should the subject decide to withdraw, documentation of early termination and any AEs and concomitant medication use should be recorded. Prior to a subject’s withdrawal from the study, an attempt will be made to conduct an early termination visit (visit 10 procedures).

The primary reason for a subject withdrawing prematurely should be selected from the following standard categories:

***Adverse Event*** – event which results in discontinuation of the study product by the subject or that in the judgment of the Investigator for the best interest of the subject requires discontinuation of study product (includes all categories of study product relatedness; Not Related, Unlikely, Possibly, Probably, and Definitely).

***Death*** – death of the subject.

***Withdrawal of Consent*** – subject desires to withdraw from further participation in the study in the absence of a medical need to withdraw determined by the Investigator.

***Lost to Follow-Up*** – subject did not return for one or more follow-up visit(s) following dispensing of study product and could not be contacted thereafter. The reason for withdrawal was unknown and could not be documented.

***Other*** – causes of premature termination from the study other than the above, such as theft or loss of study products, termination of study by Sponsor, etc.

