HDL-C	high-density lipoprotein cholesterol
hs-CRP	high-sensitivity C-reactive protein
IRB	Institutional Review Board
ITT	intention-to-treat
LDL-C	low-density lipoprotein cholesterol
LS	least squares
MCMC	Markov chain Monte Carlo
MedDRA	Medical Dictionary for Regulatory Activities
MEDFICTS	Meats, Eggs, Dairy, Fried Foods, In baked goods, Convenience foods, Table fats, Snacks
MI	multiple imputation
Non-HDL-C	Non-high-density lipoprotein cholesterol
PCSK9	proprotein convertase subtilisin kexin type 9
PD	pharmacodynamic
PP	per protocol
Q1	first quartile (25 th percentile)
Q3	third quartile (75 th percentile)
SAP	statistical analysis plan
SD	standard deviation
TEAE	treatment-emergent adverse event
TLC	therapeutic lifestyle changes
TG	triglycerides
total-C	total cholesterol
VLDL-C	very low-density lipoprotein cholesterol

DEFINITIONS

Baseline	Baseline will be the average of the values obtained during the final two pre-treatment visits for each treatment period for lipoprotein cholesterol and hsCRP, and the last value before each treatment period for apolipoproteins, PCSK9, and all omega-3 fatty acid outcomes. For the safety analysis, baseline will be the last value before each treatment period for clinical laboratory assessments and the average of the values (or average if duplicate or triplicate data are collected) obtained during the final two pre-treatment visits for each treatment period for vital signs and anthropometrics. If predose data are not collected after the washout period for Period 2 for baseline, then the last value before the first dose in Period 1 may be used as the Baseline for both periods.
Intention-to-treat population	The ITT population will include all randomized subjects.
Period	There are 2 periods defined for this study. Period 1 consists of Visits 4, 5, and 6 and Period 2 consists of Visits 8, 9, and 10.
Pharmacodynamic population	The PD population will include subjects for whom the estimation of PD parameters will be possible for 2 periods. This will be the primary population for PD analyses.
Per protocol population	The PP population will include all subjects who are included in the PD population for whom compliance for both study periods was at least 80%, and for whom no clinically important protocol violations or deviations occurred during the trial.

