7 PHARMACODYNAMIC ANALYSES

7.1 Pharmacodynamic Data

The pharmacodynamic analyses will be performed on available data from subjects in the PD population and repeated for the ITT and PP populations.

The PD outcome variables will be summarized using descriptive statistics by treatment at baseline, each postdose visit, and end of treatment (if the average) for the results, change from baseline, and percent change from baseline values. The PD outcomes will be presented in a data listing by parameter for each subject with data. Individual and mean values will be presented, as applicable.

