9.4 Changes From the Protocol

Changes made to the planned analyses in the protocol while all study staff were still blinded to the treatment sequences are summarized below.

- The baseline for Period 1 PD parameters is changed to use the last 2 values, rather than all 3 values if there is an additional screening visit. This change is to avoid bias between the calculation of baseline for both periods.
- The PP dataset and analysis will include all subjects who are included in the PD population for whom compliance for both study periods was at least 80%, and for whom

no clinically important protocol violations or deviations occurred during the trial.

- The PD dataset will include subjects for whom the estimation of PD parameters will be possible for 2 periods. PD parameters will not be estimated from measurements obtained more than three days (72 hours) after the most recent dose of study drug.
- The ITT dataset will include all subjects who are randomized to a treatment sequence.
- All secondary and exploratory outcomes are changed to percent change from baseline, rather than change from baseline as previously designated for hsCRP and all omega-3 fatty acid endpoints.
- Changes in plasma phospholipid levels of omega-3 fatty acids from baseline to Days 22 and 29 of each treatment period will be analyzed both as a concentration and a percentage of total fatty acids. These analyses will be exploratory.
- Exploratory analyses of lipids, apolipoproteins, PCSK9, hs-CRP, and plasma, plasma phospholipid, and erythrocyte membrane levels of omega-3 fatty acids will be performed using data from the first treatment period only.
- Changes in vital signs and anthropometrics will be assessed as safety outcomes.

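### Does the ITT repeat of the TG analysis need its own written rule for off-drug and missing TG values?

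*SAP*

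**What the plan says.** SAP 5.1 defines two populations that matter here. For ITT: "The ITT population will include all subjects who are randomized to a treatment sequence". The PD population, which is primary for PD analyses, needs usable data from two periods, and its paragraph adds the off-drug rule: "Measurements will not be used for PD estimation from samples obtained from subjects who have been off of study drug" for 72 hours or more. The reason given is pharmacokinetic: "The half-life of EPA from Vascepa is approximately 89 hours", against about 27 hours for EPA from MAT9001 in the fed state. SAP 9.4 repeats the rule in its PD-dataset bullet: "PD parameters will not be estimated from measurements obtained more than three days (72 hours) after the most recent dose of study drug". The separate ITT bullet in 9.4 has no such limit.

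SAP 7.1 says the PD analyses are "performed on available data from subjects in the PD population and repeated for the ITT and PP populations". SAP 7.2 puts every subject with available data into the model. SAP 5.2 provides imputation for ITT only, with the list "Multiple imputation (MI) will be used in the ITT analyses to impute missing data for the lipoprotein cholesterol, apolipoproteins, PCSK9, hsCRP" and omega-3 fatty acids. SAP 1.2 spells out lipoprotein cholesterol as five cholesterol fractions, and TG is not one of them.

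Two side provisions bear on this. Protocol 9.4 says that before withdrawal "an attempt will be made to conduct an early termination visit (visit 10 procedures", which include fasting lipids. The SAP definition of Baseline says that if Period 2 predose data are missing, "then the last value before the first dose in Period 1 may be used as the Baseline for both periods".

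**The concern.** The wording PD estimation could be stretched to cover the ITT repeat, because that repeat is a PD analysis. An off-drug TG value in ITT could then be used, dropped, or set to missing and imputed, and no sentence chooses. Read literally, 5.2 also leaves the primary outcome without an ITT imputation rule, and it does not rank the Baseline fallback against imputation.

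PP is a subset of PD, so ITT is the only population planned for the two-period TG comparison that can include subjects without two usable periods. If off-drug values are discarded, the ITT repeat nearly restates the PD result. If they are kept, it reflects what happened to subjects who stopped. In an open-label trial one would not want that choice made after seeing the results.

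**Working it through.** **1. The plan's own figure.** Inputs from SAP 2.2: difference 10, SD 28 for the between-treatment difference, 90% power; two-sided alpha 0.05 from SAP 4. Normal approximation: (28 × (1.960 + 1.282)/10)² = 82.4, so 83. The noncentral t gives exactly 85, with power 0.902, so the stated 85 reproduces. With 100 randomized, the attrition allowance is 15.

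**2. Which reading the text favours.** Both statements of the 72-hour rule are tied to the PD population. Both ITT statements lack it, and 7.2 takes all available data. Keeping observed values in ITT needs no stretching of the text; discarding them does.

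**3. Whether the missing TG label matters.** The Baseline definition uses the same shorthand, naming lipoprotein cholesterol and hsCRP but not TG, while SAP 1.2 gives TG the same two-visit baseline. That pattern points to a slip. If TG is not imputed, the mixed model uses the available data and is valid under missing-at-random. If it is imputed by MCMC, the assumption and the target are the same. Little information is at stake either way. With n = 85 complete subjects, m = 15 contributing one period (evenly split) and within-subject correlation ρ (assumed), the one-period subjects carry a share (m/2)/[(m/2) + n/(1 − ρ)] of the information:
- ρ = 0.3: 7.5/(7.5 + 121.4) = 5.8%
- ρ = 0.7: 7.5/(7.5 + 283.3) = 2.6%

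**4. Shift in the ITT ratio, kept versus discarded.** Assume Vascepa −11% (Protocol 3, from an earlier study with a very low-fat meal) and the planning difference of 10 points, so MAT9001 −21% and an on-drug ratio of 0.79/0.89 = 0.888. With kM and kV subjects out of 100 off drug in the MAT9001 or Vascepa period, the expected ratio is exp{[(100 − kM − kV) ln 0.8876 + kM·dM + kV·dV]/100}. Under full loss of effect, dM = ln(1/0.89) and dV = ln 0.79. Half loss halves the lost product's log effect.

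| Off drug | Full loss | Half loss |
|---|---|---|
| 5, all MAT9001 | +1.05 | +0.52 |
| 15, all MAT9001 | +3.19 | +1.58 |
| 5, all Vascepa | −0.52 | −0.26 |
| 15, all Vascepa | −1.54 | −0.77 |
| 8 MAT9001, 7 Vascepa | +0.95 | +0.48 |

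Shifts are in points of the ratio; plus is towards no difference. Simulation with the SAP model terms (assumed ln-scale SDs 0.20–0.25 within and 0.15–0.20 between subjects) gave standard errors of 2.5–3.4 points. The balanced case is then 0.48/3.4 = 0.14 to 0.95/2.5 = 0.38 standard errors. The extreme case is 3.19/3.4 = 0.94 to 3.19/2.5 = 1.28.

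The size depends on the assumed effect. With the earlier study's 33% and 11% (ratio 0.67/0.89 = 0.753), the same formula gives +1.8 for the 8/7 split and +4.7 for the extreme case under full loss. The latter ratio is about 0.80, still some 20 points below 1.

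**5. Power on the plan's scale** (paired t, SD 28). Kept: n = 100 and difference 10(1 − f) or 10(1 − f/2), where the off-drug share f retains none or half of the difference. Discarded: n = 100(1 − f) and difference 10.

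| f | Kept, none retained | Kept, half retained | Discarded |
|---|---|---|---|
| 5% | 0.919 | 0.932 | 0.931 |
| 10% | 0.889 | 0.919 | 0.918 |
| 15% | 0.852 | 0.905 | 0.902 |

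The largest gap is 5 percentage points; with half the difference retained there is none.

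**The case for a change.** The best case for a change is that prespecification is cheap and the choice is not neutral between products. From the SAP's half-lives, 2^(−72/89) = 57% of EPA from Vascepa remains at 72 hours but only 2^(−72/27) = 16% from MAT9001. In the extreme simulated case the chance of a significant ITT result is 62–86% with values kept and 85–98% with values discarded. Under discarding, the ITT and PD estimates correlate at 0.96–0.996, so the repeat would check little. Protocol 9.2.1 keeps randomized subjects in the study where possible, so off-drug samples at scheduled visits can occur.

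Part of this stands. The SAP is silent, and a discard rule would make the ITT repeat nearly redundant. But that weakness belongs to the less natural reading. The half-lives describe EPA level, not TG effect. The probability contrast needs 15 subjects off drug in one product's period, complete loss of effect and variances found in neither document. Complete loss generally requires both Day 22 and Day 29 to be off drug, because the endpoint averages them. The early termination visit adds little: it is to be attempted before withdrawal, nothing says the subject is by then 72 hours off drug, and no section maps an off-schedule sample into the Day 22/29 average. SAP 5.2 counts unscheduled collections among data left out of analyses. The number of off-drug samples is unknown.

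**Conclusion.** No change follows. This is missing detail in a supportive repeat with no decision rule attached, and an analyst following the text fills it sensibly: the 72-hour exclusion applies to PD and, through it, to PP; ITT uses TG as observed at the scheduled visits; and what is missing is handled under missing-at-random, by the model or by imputation. The Baseline fallback is not limited to one population, so it can be applied first, with imputation for what is still missing. TG's absence from the 5.2 list is a likely clerical slip. So is the difference between 72 hours or more in 5.1 and more than 72 hours in 9.4, which matters only for a sample at exactly 72 hours.

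The concern would be met equally by either of two opposite rules, so it does not point to a better method. At the planning ratio of 0.888 the choice moves the ITT estimate by about 1 point or less unless stops are many and concentrated in one product's period; the 3.2-point figure is an upper bound. Both rest on assumed loss of effect and on treating the whole attrition allowance as off-drug subjects with samples. The primary PD comparison does not depend on the ITT handling.
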